## SYNOPSIS

Title of study: A Double-blind, Placebo-controlled, Phase 2a Proof-of-concept Trial of Dalcetrapib in Patients with Confirmed Mild to Moderate COVID-19
Indication: Coronavirus disease of 2019 (COVID-19)
Number of Investigators and study centers: Up to 60 sites in the United States and Canada, site distribution will depend on the pandemic status.
Development Phase: 2a
Objectives: The primary efficacy objective of the study is: 

• To evaluate the time to sustained clinical resolution of symptoms in patients with confirmed, mild to moderate, symptomatic COVID-19 treated with dalcetrapib. Sustained clinical resolution is defined as occurring when no key COVID-19 related symptom has a score higher than 1 over a 72-hour period (as documented using an electronic patient-reported outcome [ePRO] instrument), except for sense of smell and taste (items 13 and 14) where the score should be 0 over a 72-hour period. The time to resolution will be taken as the time from randomization until the first day of the last 72-hour period where the patient meets the definition of resolution within 28 days. Patients who do not meet the definition of resolution 28 days after randomization will be considered not resolved.

 The secondary efficacy objectives of the study are: 

• To evaluate the change from baseline in COVID-19 symptom severity score at all collected time points

• To evaluate time to complete clinical resolution, defined in the same way as the primary endpoint, but considering that all symptoms must resolve to a score of 0 for 72 hours

• To evaluate the time to viral clearance using SARS-CoV-2 polymerase chain reaction (PCR)

• To evaluate change from baseline in log10 viral load

• To evaluate the World Health Organization (WHO) clinical outcome scale (9-point scale) at Day 3, Day 5, Day 10, and Day 28

• Rate of hospitalization through Day 28

• To evaluate the rate of progression to oxygen therapy through Day 28

• To evaluate the duration of hospitalization

• To evaluate the mortality rate by Day 28

The safety objective of the study is:

- To assess the safety and tolerability of dalcetrapib active doses compared to placebo in patients with COVID-19

The pharmacokinetics (PK) objective of the study is:

- To evaluate the PK of dalcetrapib in patients with COVID-19

### **Methodology/study design:**

This is a randomized, double-blind, multicenter Phase 2a proof-of-concept study in outpatients with confirmed, mild to moderate, symptomatic COVID-19. Electronic informed consent must be obtained from all patients or their legally authorized representative during screening before any study-related procedures are performed. The Screening/Baseline assessments may be performed at the study site or as a home visit.

A total of 208 patients will be randomized to receive 900, 1800, or 3600 mg of dalcetrapib or placebo once daily (52 patients to each of 900 mg, 1800 mg, 3600 mg and placebo) for 10 days. Patients will be randomized and receive first dose of study drug within 72 hours of receiving a positive PCR or Point-of-care test for SARS-CoV-2. Patients need to have at least two of the 14 common COVID-19-related symptoms described in the inclusion criteria rated as mild or moderate, as evaluated by ePRO assessment. Symptoms will be assessed at each study visit daily for the first 10 days, then at Day 14 and Day 28, and as clinically indicated.

Symptoms will be evaluated as absent, mild, moderate, or severe depending on their impact on activities of daily living. SARS-CoV-2 viral loads will be obtained by both saliva (Oragene) collection and mid-turbinate nasal swab self-collection under supervision of a healthcare professional (virtual or home visit) at Screening/Baseline, Day 1, Day 3, Day 5, Day 7, Day 10, and Day 28. Patients who require hospitalization after initiation of study treatment will be followed for safety assessment through Day 28.

The study will be overseen by an independent Data Monitoring Committee (DMC). The DMC will review the safety data throughout the study. The DMC and Sponsor will review efficacy data at the interim analysis and at the end of the study. A DMC Charter, which includes detailed processes, will be prepared. One interim analysis will be conducted once 97 resolution events have been observed.

All patients will be closely monitored for adverse events (AEs) from informed consent for at least 18 days after the final dose of study treatment (until Day 28±2). Patients who withdraw early from the study will have follow-up phone calls to collect safety data until End of Study on Day 28±2. On days of laboratory assessments and PK sample collection, outpatient subjects may have a home visit.

### **Study Visit Procedures**

Study visits (virtual, study site or home visits by a healthcare professional) will take place on Days 1, 3, 5, 7, 10, 14, and 28. Screening/Baseline assessments may all be performed on the same calendar day and may be performed at the study site or as a home visit. For visits which include bloodwork, sample collection may be done by a visiting healthcare professional or at the study site (as long as the patient has no worsening of respiratory symptoms or no fever within 24 hours). Other visits may be conducted remotely using telemedicine.

The samples for viral load testing will be both saliva (Oragene) collection and mid-turbinate nasal swab self-collected under supervision of a healthcare professional. Telemedicine visits such as phone calls or other digital media are to be utilized as much as possible.

### **Number of patients:**

It is anticipated that 208 patients will be randomized into the study in a 1:1:1:1 ratio to 900, 1800, or 3600 mg dalcetrapib or placebo.

### **Determination of Sample Size:**

The purpose of the proof-of-concept study is to identify whether there is sufficient promise of efficacy to justify conducting a Phase 3 study in a larger sample size and to determine efficacious dose to be used in Phase 3. While the entirety of data will be considered at the end of study, the sample size has been chosen to ensure that a positive trend will be present with alpha of 0.2 when considering the two highest doses combined compared to placebo. One-hundred twenty-seven (127) resolution events provides 80% power to demonstrate a positive trend if the average hazard ratio (HR) of the two dalcetrapib groups is 1.4 relative to placebo. Allowing for 20% of patients not resolving, 156 patients (52 per treatment arm) will be enrolled across the two highest dose levels and placebo arms, and an additional 52 will be randomized to 900 mg for a total sample size of 208 patients. One interim analysis will be conducted once 97 resolution events have occurred to allow 73 resolution events to have occurred in the two highest dose levels and placebo arm. At the interim analysis, if the average HR of the two highest dose levels relative to placebo is greater than 1.45, the study will stop due to efficacy and the program will be able to proceed directly to Phase 3. At the interim analysis, if the average HR of the two highest dose levels relative to placebo is between 1.0 and 1.45, the study will continue enrollment until 169 resolution events have occurred. At the interim analysis, if the average HR of the two highest dose levels is less than 1.0, the study will be stopped for lack of efficacy. The final analysis will be performed at an alpha of 0.186. These boundaries were determined by setting the efficacy boundary to follow the power family boundary with  $\rho=2$  and the futility boundary is manually set to HR=1.

### **Diagnosis and criteria for inclusion and exclusion:**

The following are the inclusion criteria:

1. Willing and able to provide informed consent
2. Male or female patients > 18 years of age on the day of informed consent
3. Have received a confirmed diagnosis of COVID-19 (positive for SARS-CoV-2), as assessed by PCR or point-of-care within 72 hours of first dose on Day 1
4. Have mild to moderate signs or symptoms of COVID-19 with onset within 5 days of first dose on Day 1, at least two of the following symptoms:
  - stuffy or runny nose
  - sore throat
  - shortness of breath
  - cough
  - fatigue
  - myalgia
  - headache
  - chills or shivering
  - feeling hot or feverish
  - nausea
  - vomiting
  - diarrhea
  - anosmia
  - ageusia

5. Outpatient with COVID-19 disease (not requiring oxygen therapy [WHO COVID-19 Clinical Improvement Ordinal Scale, score of 3])
 
6. Patient is aware of the investigational nature of this study and willing to comply with protocol treatments, blood tests, and other evaluations listed in the ICF.

--

The following are the exclusion criteria:

- 1. Females who are pregnant (negative pregnancy test required for all women of child-bearing potential at Screening) or breast-feeding
- 2. Male patients and women of childbearing potential (women who are not surgically sterile or postmenopausal defined as amenorrhea for >12 months) who are not using at least one protocol-specified method of contraception
- 3. Severe COVID-19 disease as defined by the WHO COVID-19 Clinical Improvement Ordinal Scale, scores of 5 (non-invasive ventilation or high-flow oxygen), 6 (intubation and mechanical ventilation), or 7 (ventilation + additional organ support pressors, renal replacement therapy [RRT], extracorporeal membrane oxygenation [ECMO])
- 4. Expected survival less than 72 hours
- 5. Peripheral capillary oxygen saturation (SpO2) <90% while breathing room air
- 6. Treatment with other drugs thought to possibly have activity against SARS-CoV-2 infection like remdesivir, favipiravir, within 7 days prior to enrollment or concurrently
- 7. History of abuse of drugs or alcohol that could interfere with adherence to study requirements as judged by the Investigator
- 8. Use of any other concurrent investigational drugs while participating in the present study
- 9. Patient requires frequent or prolonged use of systemic corticosteroids ( $\geq 20$  mg of prednisone/day or equivalent for >4 weeks) or other immunosuppressive drugs (e.g., for organ transplantation or autoimmune conditions)
- 10. Known renal disease with an estimated glomerular filtration rate (eGFR) <50 mL/min based on local laboratory results
- 11. Patients with clinically apparent liver disease, e.g., jaundice, cholestasis, hepatic synthetic impairment, or active hepatitis
- 12. Alanine transaminase (ALT) or aspartate transaminase (AST)  $>3 \times$  upper limit of normal (ULN) or alkaline phosphatase or bilirubin levels  $> 2 \times$  ULN based on local laboratory results
- 13. Co-administration of clinical doses of orlistat with dalcetrapib
- 14. Inability to swallow oral medications or a gastrointestinal disorder with diarrhea (e.g., Crohn's disease) or malabsorption at Screening
- 15. Any other clinically significant medical condition or laboratory abnormality that, in the opinion of the Investigator, would jeopardize the safety of the patient or potentially impact patient compliance or the safety/efficacy observations in the study
- 16. History of an allergic reaction or hypersensitivity to the study drug or any component of the study drug formulation.

**Test products, dose, and mode of administration:**

Dalcetrapib in a dose of 900, 1800, or 3600 mg (300 mg tablets) administered once daily, orally, for 10 days

**Reference therapy, dose, dose form, and mode of administration:**

Matching placebo tablets administered once daily, orally, for 10 days

### **Duration of patient participation in study:**

Planned screening duration: 1 to 2 days  
Planned treatment duration: 10 days  
Planned follow-up duration: 18 days  
Total duration of study participation: up to 30 to 32 days

### **Study populations:**

**Intention-to-treat (ITT) Population:** The Intent to Treat Population will include all participants who received at least 1 dose of study drug. Participant data will be summarized by treatment assigned.

**Per Protocol (PP) population:** All participants from the ITT population who have no important study protocol deviations during the study and who received at least 1 dose of study drug. Patients with any important protocol deviations shall be excluded from the PP population prior to database lock.

**Safety Population:** The Safety Population will include all participants who received at least 1 dose of study drug. Participant data will be summarized by actual treatment received.

**Pharmacokinetic Population:** The PK Population will include all participants who received at least 1 dose of study drug, had at least one measurable plasma concentrations, and had no protocol deviations thought to impact the PK of study drug.

### **Evaluation: Efficacy**

#### Primary Endpoint:

- Time to sustained clinical resolution.  
Sustained clinical resolution is defined as occurring when no key COVID-19 related symptom has a score higher than 1 over a 72-hour period (as documented using an electronic patient-reported outcome [ePRO] instrument), except for sense of smell and taste (items 13 and 14) where the score should be 0 over a 72-hour period. The time to resolution will be taken as the time from randomization until the first day of the last 72-hour period where the patient meets the definition of resolution within 28 days. Patients who do not meet the definition of resolution 28 days after randomization will be considered not resolved.

#### Secondary endpoints:

- Time to complete clinical resolution
- Change from baseline in COVID-19 total symptom score
- Scoring of WHO Clinical Outcome Scale (9-point scale)
- Rate of hospitalization
- Rate of progression to oxygen therapy
- Duration of hospitalization
- Time to viral clearance based on PCR test for SARS-CoV-2
- Change from baseline in log10 viral load
- Mortality rate

### **Evaluation: Safety**

The number and percentage of patients with treatment-emergent AEs (TEAEs), serious AEs (SAEs), TEAEs related to study treatment, SAEs related to study treatment, TEAEs leading to treatment discontinuation, and TEAEs leading to death will be summarized by system organ class (SOC), preferred term (PT), and treatment group. In addition, the severity of TEAEs and relationship to study treatment will be summarized by SOC, PT, and treatment group.

Test values and change from baseline will be summarized descriptively by treatment group for specific laboratory test results and vital signs. Where applicable, shift tabulations by treatment group will be presented.

### **Evaluation: Pharmacokinetics**

Dalcetrapib concentrations will be determined in the PK samples collected according to the Schedule of Assessments.

### **Statistical methods:**

Continuous variables will be summarized by the standard descriptive statistics: number of patients (n), mean, standard deviation, median, minimum, and maximum for baseline variables, and n, mean, standard error, and confidence interval (CI) for outcome measures. Frequency of patient or events and percentages will be summarized for categorical variables. Time to event variables will be summarized using Kaplan-Meier methods.

Unless otherwise specified, all regression models will be stratified by maximum symptom severity at baseline (presence vs absence of moderate or severe symptoms) and by age ( $\leq 65$  years vs  $> 65$  years), and Wald p-values will be considered primary.

### **Efficacy Analysis**

The analysis of treatment efficacy will be based on the Intent-to-Treat Population. The PP population will be used for secondary analysis. This section is a summary of the planned efficacy analyses of the most important efficacy endpoints including primary and key secondary efficacy endpoints.

### **Analysis of Primary Endpoints**

#### ***Time to Sustained Clinical Resolution***

The primary endpoint is time to sustained clinical resolution as determined by symptom score. The primary analysis of this endpoint will be performed on the ITT population. Time to sustained clinical resolution will be summarized by treatment group using Kaplan-Meier methods. Median and associated 95% CI, 25-75 percentiles, and minimum and maximum values will be presented. The number and percentage of patients whose symptoms resolved, and patients censored will be presented.

The differences in time to sustained clinical resolution between the treatment groups will be evaluated using a 2-sided log-rank test, stratified for baseline symptom severity (presence vs absence of moderate or severe symptoms) and by age ( $\leq 65$  years vs  $> 65$  years). The combined two highest treatment groups will be compared to placebo in addition to the comparison of individual doses.

## **Analysis of Secondary Efficacy Endpoints**

### ***Time to Complete Clinical Resolution***

Time to complete clinical resolution will be analyzed using the same model as time to sustained clinical resolution, but with all symptoms required to have resolved to a score of 0 rather than 1.

### ***Change from Baseline in COVID-19 Total Symptom Severity Score***

COVID-19 total symptom severity score will be summarized by treatment group using descriptive statistics (N, mean, median, standard deviation, minimum, and maximum) for each visit as well as for changes from baseline (N, mean, standard error, CI). A Mixed-Effect Model Repeated Measure (MMRM) will be performed to analyze the average difference between treatment groups over 28 days and at the designated assessment days.

### ***Scoring of WHO Clinical Outcome Scale (9-point scale)***

The number and percentage of patients for each WHO clinical outcome score will be summarized. An ordinal logistic regression analysis for the specified time points will be presented as odds ratio, with associated 95% CI and p-value.

### ***Rate of Hospitalization through Day 28***

The analysis of this endpoint will be performed on the ITT population. The number and percentage of patients who were hospitalized and reason for hospitalized will be presented. The percentage of patients who were hospitalized will be compared using a logistic regression analysis for specified time points. The results will be presented as odds ratios, with associated 95% CIs and p-value.

### ***Rate of Progression to Oxygen Therapy through Day 28***

The analysis of this endpoint will be performed on the ITT population. The number and percentage of patients who progress to oxygen therapy and type of oxygen therapy will be presented. The percentage of patients who had progressed to oxygen therapy will be compared using a logistic regression analysis for specified time points. The results will be presented as odds ratios, with associated 95% CIs and p-value.

### ***Duration of Hospitalization***

The duration of hospitalization will be performed on the ITT population. Duration of hospitalization will be summarized by treatment group using descriptive statistics (N, mean, median, standard deviation, standard error, CI, minimum, and maximum). Linear regression will be performed to analyze the difference between treatment groups. The results will be presented as mean treatment difference with associated 95% CI and p-value.

### ***Mortality Rate***

The analysis of this endpoint will be performed on the ITT population. The number and percentage of patients who died and reason for death will be presented. The percentage of patients who died will be compared using a logistic regression analysis for specified time points. The results will be presented as odds ratios, with associated 95% CIs and p-values.

### ***Time to Viral Clearance based on PCR Test for SARS-CoV-2***

The time to viral clearance based on PCR test for SARS-CoV-2 will be performed on the ITT population. Time to viral clearance will be summarized by treatment group using Kaplan-Meier methods. Median and associated 95% CI, 25-75 percentiles, and minimum and

maximum values will be presented. The number and percentage of patients who do not show virus, show virus, and patients censored will be presented.

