### **8.3. General Considerations**

Continuous variables will be summarized by the standard descriptive statistics: number of patients (n), mean, standard deviation, median, minimum, and maximum for baseline variables, and n, mean, standard error, and confidence interval (CI) for outcome measures. Frequency of patient or events and percentages will be summarized for categorical variables. Time to event variables will be summarized using Kaplan-Meier methods.

Unless otherwise specified, all regression models will be stratified by maximum symptom severity at baseline (presence vs absence of moderate or severe symptoms) and by age ( $\leq 65$  years vs  $> 65$  years), and Wald p-values will be considered primary.

The statistical analysis plan will be finalized prior to unblinding and it will include a more technical and detailed description of the statistical analyses.

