## 1 INTRODUCTION

The purpose of this statistical analysis plan (SAP) is to present the statistical methodology that will be used for the final analysis of DalCor Pharmaceuticals DAL-401. This plan also provides a description of the tables, figures and listings that will be included in the final statistical report. It is based on the protocol dated 22-OCT-2020 and on the annotated case report form (CRF) version 1.0. In case of differences in terms of descriptions or explanations between the SAP and the clinical protocol, the SAP will supersede the protocol. Any deviation to this SAP would be reported in the statistical report.

Since the protocol was developed and discussed with the regulatory authorities, a greater understanding of COVID-19 and clinical trials in COVID-19 has emerged. New variants have also been observed and their clinical course needs to be taken into consideration. Based on this emerging knowledge, a higher emphasis will be placed on viral load analyses when interpreting the data and deciding on POC in this study. Less emphasis will therefore be placed on the current primary endpoint of Patient Reported Outcomes and endpoints that look at changes in symptoms of COVID-19. Certain symptoms such as loss of taste and loss of smell as well as cough are chronic symptoms which may not resolve over the course of a 28-day study. In view of this the endpoints evaluating symptoms will not include taste, smell or cough in some analyses.

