## 2 STUDY DESCRIPTION

### 2.1 Study Design

This is a randomized, double-blind, multicenter Phase 2a proof-of-concept study in outpatients with confirmed, mild to moderate, symptomatic COVID-19. Electronic informed consent must be obtained from all patients or their legally authorized representative during screening before any study-related procedures are performed. The Screening/Baseline assessments may be performed at the study site or as a home visit.

A total of 208 patients will be randomized to receive 900, 1800, or 3600 mg of dalcetrapib or placebo once daily (52 patients to each of 900 mg, 1800 mg, 3600 mg and placebo) for 10 days. Patients will be randomized and receive first dose of study drug within 72 hours of receiving a positive PCR or Point-of-care test for SARS-CoV-2. Patients need to have at least two of the 14 common COVID-19-related symptoms described in the inclusion criteria rated as mild or moderate, as evaluated by ePRO assessment or eCRF. Symptoms will be assessed at each study visit daily for the first 10 days, then at Day 14 and Day 28, and as clinically indicated. Symptoms will be evaluated as absent, mild, moderate, or severe depending on their impact on activities of daily living. SARS-CoV-2 viral loads will be obtained by both saliva (Oragene) collection and mid-turbinate nasal swab self-collection under supervision of a healthcare professional (virtual or home visit) at Screening/Baseline, Day 1, Day 3, Day 5, Day 7, Day 10, and Day 28. Patients who require hospitalization after initiation of study treatment will be followed for safety assessment through Day 28.

The study will be overseen by an independent Data Monitoring Committee (DMC). The DMC will review the safety data throughout the study. The DMC and Sponsor will review efficacy data at the interim analysis and at the end of the study. A DMC Charter, which includes detailed processes, will be prepared. One interim analysis will be conducted once 120 patients have a follow-up time of 28 days.

All patients will be closely monitored for adverse events (AEs) from informed consent for at least 18 days after the final dose of study treatment (until Day 28±2). Patients who withdraw early from the

study treatment will have follow-up phone calls to collect safety data until End of Study on Day 28±2. On days of laboratory assessments and PK sample collection, outpatient subjects may have a home visit.

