##### **6.4.1 Primary Analysis**

The primary endpoint is time to sustained clinical resolution of symptoms (excluding cough, sense of smell and taste) as determined by symptom score. Sustained clinical resolution of symptoms (excluding cough, sense of smell and taste) is defined in Section 4.1. Time to sustained clinical resolution will be calculated as date of resolution – date of randomization + 1. Subjects who did not resolve will be censored at the last time point where they were not resolved [see Section 9 Appendix 1]. The number and percentage of patients whose symptoms resolved will be presented, and to summarize the time to resolution, censored subjects will be imputed with a time to resolution of 29 days and simple medians with 80% confidence intervals will be provided.

The differences in time to sustained clinical resolution of symptoms (excluding cough, sense of smell and taste) between the treatment groups will be evaluated using 2-sided log-rank tests. The combined two highest treatment groups will be compared to placebo in addition to the comparison of individual doses.

The cumulative incidence curve for sustained clinical resolution (excluding cough, sense of smell and taste) will also be presented using 1 – Kaplan-Meier estimates(Section 7, Figure 2). Should there be several deaths, the cumulative incidence curve will be presented under a competing risk model.

A listing with the score of each symptom at each time point will be provided (Section 7, Listing 7).

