##### **6.4.2 Key Secondary Analysis**

#### 6.4.2.1 Change from Baseline in log10 Viral Load

Log10 viral load, as assessed using the saliva and as assessed using the nasal swab, will be summarized by treatment group using descriptive statistics (N, mean, median, standard deviation, minimum, and maximum) for each visit as well as for changes from baseline where an 80% CI will also be presented.

Mean changes from baseline will be analyzed using a repeated measures ANCOVA model including effects of treatment, visit (Day 3, Day 5, Day 10 and Day 28/EOS), and treatment-by-visit interaction, as well as baseline value of log10 viral load and baseline value of log10 viral load-by-visit-interaction. An unstructured covariance structure will be used to model the within-patient errors and the Kenward-Roger approximation will be used to estimate denominator degrees of freedom. The combined two highest treatment groups will be compared to placebo in addition to the comparison of individual doses at the following study visits (Day 3, Day 5, Day 10 and Day 28/EOS).

Since oragene and nasal samples are collected by the subjects themselves (visit identifiers may be unreliable), an algorithm (presented in Appendix 2) was developed to classify the day of assessment into their respective visit identifiers. This algorithm is based on the fact that Day 1 corresponds to the date of the first dose and as such, will be used as baseline when available. This is in alignment with the study protocol that identifies Day 1 as the date of first dose. It is understood that all protocol assessments collected on Day 1 were to be done PRIOR to the first dose. Therefore, Day 1 will correspond to baseline when available. Please refer to Appendix 2 for more details.

A plot of mean change from baseline in log10 viral load with 80% CI at each study visit will also be presented (Section 7, Figure 4).

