### 6.4.3 Other Secondary Analysis

#### **6.4.3.1 Time to Viral Clearance Based on PCR Test for SARS-CoV-2**

Each subject will be tested to determine if the subject has COVID-19 by obtaining a PCR or rapid antigen test as it confirms the presence of SARS-CoV-2. A subject will be considered to no longer have COVID-19 if two consecutive PCRs do not detect SARS-CoV-2. Time to viral clearance using PCR test for SARS-CoV-2, as assessed using the saliva and using the nasal swab, will be calculated as date of the first negative PCR test for SARS-CoV-2 – date of randomization + 1. Subjects who did not obtain two consecutive negative PCRs will be censored at the date of study completion.

Same statistical methods as those described in section 6.4.1 will be used to analyze the time to viral clearance.

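### SAP 6.4.3.1 compares time to viral clearance by an unadjusted log-rank test although baseline viral load is available; the test is valid, but it may give up some power

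*Protocol*

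**What the plan says.** The protocol (Synopsis and 8.4.2.8) plans only a description of viral clearance: "Time to viral clearance will be summarized by treatment group using Kaplan-Meier methods". The test comes from SAP 6.4.3.1: "Same statistical methods as those described in section 6.4.1 will be used to analyze the time to viral clearance". In SAP 6.4.1, differences "between the treatment groups will be evaluated using 2-sided log-rank tests", and no stratum or covariate is named. The SAP governs where the two documents differ (SAP 1): "In case of differences in terms of descriptions or explanations between the SAP and the clinical protocol, the SAP will supersede the protocol".

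Both specimens are scheduled for collection "at Screening/Baseline, Day 1, Day 3, Day 5, Day 7, Day 10, and Day 28" (SAP 2.1). Appendix 2 of the SAP fixes the baseline value as Day 1, or screening if there is no Day 1 sample. On those same samples, SAP 6.4.2.1 models change in log10 viral load with treatment and visit terms, "as well as baseline value of log10 viral load and baseline value of log10 viral load-by-visit-interaction".

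Protocol 8.3 has a general stratification rule, "Unless otherwise specified, all regression models will be stratified by maximum symptom severity at baseline", with age as the second factor. Baseline viral load is not among those factors, so that rule would not have brought it into the clearance comparison.

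**The concern.** Clearance is dated at the first of two consecutive negative PCRs, so it is a threshold crossing of the viral-load trajectory. At a given rate of decline, a patient who starts higher takes longer to reach the limit. Baseline load in the same specimen is therefore expected, on mechanistic grounds, to predict clearance time. The SAP uses it for the quantitative endpoint on those samples but not for the time-to-event endpoint.

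A log-rank test that leaves a prognostic factor unused keeps its type I error but can lose power. SAP 1 says that viral-load analyses will carry more weight in deciding proof of concept. A real difference in clearance would then be somewhat more likely to go undetected than it need be.

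**Working it through.** **The plan's own power figure.** None is stated for clearance. The only one is for symptom resolution: 127 events, 80% power, hazard ratio (HR) 1.4, alpha 0.2. It reproduces as a one-sided 0.2 two-look design with 2:1 allocation. Alpha spent at the interim is 0.2 × (73/127)² = 0.0661, so z = 1.506. The interim boundary is exp(1.506/√(73 × 2/9)) = 1.453 (stated 1.45). The final nominal alpha is 0.1862 (stated 0.186) and power is 80.0%. None of this carries over to clearance.

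**Inputs from the documents.** 104 v 52 patients in the main contrast; two-sided 0.20 (SAP 6.2); the sampling days; two consecutive negatives. A first negative at Day 28 has no later scheduled sample to confirm it. All other inputs below are assumptions.

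**Check 1: proportional hazards.** Clearance hazard = λ·exp(ln 1.4 × arm − β × v), where v is standardised baseline load. λ is set so that 60% or 40% of placebo patients clear by Day 10. Clearance is recorded on Days 3, 5, 7 or 10, with no dropout. The log-rank is compared with a Cox model adjusted for v (Efron ties, Wald test). There were 3,000 runs per cell, and rejections in the beneficial direction were counted.

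| Clearance HR per 1 SD lower baseline load | 60% clear: log-rank → adjusted | Gain (points) | 40% clear: log-rank → adjusted | Gain (points) |
|---|---|---|---|---|
| 1.00 | 62.6% → 61.4% | −1.2 | 50.2% → 49.4% | −0.8 |
| 1.28 | 60.2% → 60.8% | +0.6 | 50.6% → 50.8% | +0.2 |
| 1.65 | 55.0% → 59.7% | +4.7 | 48.5% → 50.8% | +2.3 |
| 2.12 | 49.6% → 58.8% | +9.2 | 42.9% → 49.3% | +6.4 |
| 2.72 | 43.7% → 55.8% | +12.1 | 39.0% → 48.5% | +9.5 |
| 4.48 | 33.2% → 45.8% | +12.6 | 33.6% → 43.9% | +10.3 |

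**Check 2: threshold crossing.** Time to the limit = (baseline − limit)/slope. Assume a mean baseline of 6 log10, a limit of 2.5, and a decline of 0.5 log10/day, 20% faster on drug. The average placebo patient takes (6 − 2.5)/0.5 = 7 days; on drug, 3.5/0.6 = 5.8 days. For placebo:

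- Baseline ±1 SD (1.5): 2/0.5 = 4 to 5/0.5 = 10 days.
- Slope ±1 SD (0.15): 3.5/0.65 = 5.4 to 3.5/0.35 = 10 days.
- Slope ±1 SD (0.25): 3.5/0.75 = 4.7 to 3.5/0.25 = 14 days.

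So baseline load is the larger source of spread at slope SD 0.15, and decline rate is the larger source at 0.25.

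The next table gives simulated power for the plain log-rank and for the log-rank stratified by tertile of baseline load, in patients detectable at baseline, with sampling noise 0.8 log10.

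| Slope SD | Baseline SD 1.2 | Baseline SD 1.5 | Baseline SD 2.0 |
|---|---|---|---|
| 0.15 (1,500 runs) | 72% → 79% | 68% → 78% | 58% → 73% |
| 0.25 (2,500 runs) | 54.8% → 57.3% | 51.0% → 56.3% | 49.0% → 55.2% |

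Other runs of this model gave 74% → 81%, 68% → 77% and 57% → 70% in the favourable setting. A further set gave gains of about 8 to 13 points at slope SD 0.15 and about −1 to +4 at 0.25. With noise 1.2 and slope SD 0.25 the gain was 2 points (51% → 53%). The single 15-point gain (58% → 73%) does not clearly differ from 13: one power estimate has a standard error of √(0.58 × 0.42/1,500) = 1.3 points. Rejection under no effect was 18–22% for the plain test and 19–21% for the stratified test.

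**The case against.** The case for leaving the SAP alone is a fair one.

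- **The test is valid.** A reader might infer bias or inflated type I error. Randomization rules that out, and the simulations show rejection near 20% either way. A reader might also infer that a reported effect would be pulled toward no difference, but SAP 6.4.1 plans percentages, medians, log-rank p-values and a cumulative incidence curve. No hazard ratio is planned for clearance.
- **The strength of the predictor is not documented.** It is tempting to say that baseline load largely fixes clearance time. Nothing in the documents says so, and variation in decline rate competes with it. The favourable gains come from assuming that this variation is small.
- **The endpoint is low in the order.** SAP 4.2 lists clearance among the other secondary endpoints. Change in log10 viral load is a key secondary endpoint and already adjusts for baseline. The emphasis in SAP 1 does not mean that a missed clearance p-value would decide proof of concept.
- **Baseline is not guaranteed in every patient.** Appendix 2 provides for a missing Day 1 sample, and SAP 6.4.2.1 admits that visit labels on self-collected samples may be unreliable. Check 2 was restricted to patients detectable at baseline; the ITT analysis is not.

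All four points stand. They limit the size and importance of the matter. They do not explain why a covariate that is scheduled, derived and used in the companion model is left out here.

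**Conclusion.** The point holds as an efficiency improvement, not as an error. Under the governing SAP, clearance is compared in each specimen without using baseline load. Using it would change power by about −1 to +13 percentage points at two-sided 0.20. The gain is about 2 to 12 points if clearance HR per SD of baseline load is 1.65 to 2.72, and nil up to about 1.28. This range rests on assumed effect sizes, clearance proportions, decline rates and noise. The one viral-load figure in the SAP, the 2228 cp/mL example in 6.2.2.1, does not narrow it.

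A reader might take the protocol itself to plan an unadjusted log-rank test for clearance. Its clearance section contains no test, so the point belongs to SAP 6.4.3.1 and 6.4.1.

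**What to change.** In SAP 6.4.3.1, before unblinding:

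1. Make the clearance comparison for each specimen a log-rank test stratified by category of baseline log10 viral load in that specimen, for example tertiles, using the Appendix 2 baseline (Day 1, else screening).
2. State where patients with undetectable or missing baseline are placed, for example in their own stratum. SAP 6.2.2.1 codes no detected virus as 1 cp/mL, which is 0 log10, while its example of a detected result below the limit becomes log10(1114) = 3.05. Categories avoid treating that gap as a real distance.
3. Keep the unstratified log-rank as supportive.

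The cost is a few sentences and a STRATA statement, with no new data or patients. The downside is small. Tertiles leave about 156/3 = 52 patients per stratum in the main contrast and 104/3 ≈ 35 for a single dose against placebo, and an undetectable or missing stratum could be sparse. If baseline load is not prognostic, about 1 point of power is lost. If a Cox model is used instead, its hazard ratio is conditional on baseline load and should be labelled so.
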